## Data Collection

1.0 Indicate what data will be collected.

Data will be collected by a research staff member or a co-investigator. Please see the data collection sheets for further detail.

1. Day of Surgery in the holding area - patient demographics (name, age, sex, race, BMI); NRS pain score at rest, during ambulation, while bending knee
2. Day of Surgery upon spinal resolution - Procedure length; ASA classification; tourniquet time; NRS pain score at rest, during ambulation, while bending knee; painOUT; opioid consumption; PT data sheet (assessing lines, nausea, vomiting, dizziness, pain NRS post-PT, buckling, transfer details, ambulation details, stair details, straight leg raise)
3. POD 1 - NRS pain score at rest, during ambulation, while bending knee; painOUT; opioid consumption; PT data in the morning, afternoon, and evening (assessing lines, nausea, vomiting, dizziness, pain NRS post-PT, buckling, transfer details, ambulation details, stair details, straight leg raise; was discharge criteria met (time and date)?); Hospital DC lag questionnaire
4. POD 2 - NRS pain score at rest, during ambulation, while bending knee; painOUT; opioid consumption; PT data in the morning, afternoon, and evening (assessing lines, nausea, vomiting, dizziness, pain NRS post-PT, buckling, transfer details, ambulation details, stair details, straight leg raise; was discharge criteria met (time and date)?); Hospital DC lag questionnaire
5. Knee Society Score - Both pre-operatively and at first post operative surgeon's office visit (obtained through Total Joint Registry)

2.0 Who will collect the data:

[name].

[name], PhD IRB Vice Chair

Print: 2014-018 - The Combination of Adductor Canal Block and Periarticular Injectio...

Page 17 of 37

<https://ecap.hss.edu/eCAP/ResourceAdministration/Project/PrintSmartForms?Project=com.w...> 8/22/16

ID: 2014-018 Section: PART II - Clinical Research Proposal - Interventions or Observations

[name] Research Assistant

[name] Physical Therapist

[name]

[name]

[name]

[name]

[name] Assistant Director, Research

[name]

[name] Physical Therapist

[name] Research Associate

[name]

[name]

[name]

[name] Regional Anesthesia fellow

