## Sample Size and Data Analysis

Support estimates with evidence from the literature of prior studies and perform an appropriate sample size calculation.

Print: 2014-018 - The Combination of Adductor Canal Block and Periarticular Injectio...

Page 20 of 37

<https://ecap.hss.edu/eCAP/ResourceAdministration/Project/PrintSmartForms?Project=cm.w...> 8/22/16

ID: 2014-018 Section: PART II - Clinical Research Proposal - Sample Size & Data Analysis

For hypothesis testing (e.g., the calculation of p-values using statistical tests), you need to

estimate your available sample size and calculate the effect size that will be detectable using your proposed statistical analysis plan. This also applies to a case series where you

plan hypothesis testing.

1.0 If you have consulted with a statistician, please indicate their name:

[name]

2.0 Proposed sample size analysis, include the following:

- Student's t-test, ANOVA, chi-square, regression, etc;
- Alpha level;
- Beta or power level;
- Primary outcome variable estimate (mean +/-s.d. for continuous outcome, frequency/percentage for categorical variable);
- Number of groups being compared (use 1 for paired analysis within the same subjects);
- Effect size or change expected between groups;
- Resulting number per group

A previous trial at HSS found the standard deviation (SD) in time until ready for discharge (based on achievement of PCA, nausea, diet, urination, pain, surgical, medical, and PT criteria) for TKR patients receiving periarticular injections to be 0.83 days (YaDeau, 2013). This SD was considered to be a reasonable estimate of the variability in the time until patient is able to independently negotiate stairs within the periarticular injection alone group. A 0.5 day difference in mean time until patient is able to independently negotiate stairs between the periarticular injection alone and periarticular injection + ACB groups was determined to be clinically meaningful. With two-sided alpha set at 0.05, power at 0.8, and the addition of 10% more patients to account for potential protocol violations, the number of patients required for a two-sample t-test is 53 patients per group (106 patients total\*).

\*Our a priori sample size calculation assumed that 96 of 106 enrolled patients would adhere to trial protocol. However, ultimately only 92 out of 106 patients adhered to trial protocol. Therefore, we plan to continue enrollment up to 114

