patients until 96 patients without protocol deviations are enrolled.

3.0

**Data Analysis:** describe how the primary outcome will be analyzed and what types of statistical calculations will be used. Do the same for each secondary outcome. Reiterate briefly the main analysis to be done, which groups, which variables, possible confounders. Address how possible confounders will be identified and handled in analysis:

Print: 2014-018 - The Combination of Adductor Canal Block and Periarticular Injectio...

Page 21 of 37

<https://ecap.hss.edu/eCAP/ResourceAdministration/Project/PrintSmartForms?Project=cm.w...> 8/22/16

ID: 2014-018 Section: PART II - Clinical Research Proposal - Sample Size & Data Analysis

The primary outcome, time until the patient is able to independently negotiate stairs, will be compared between the periarticular injection alone and periarticular injection + ACB groups with a two-sample t-test or Wilcoxon rank-sum test, depending upon the distribution of the data. The precision of the estimate of the difference between groups will either be reported as a 95% confidence interval for the difference in means or the Hodges-Lehmann estimate of location shift. Longitudinal secondary outcome data (NRS pain scores, narcotic consumption, incidence of side effects, painOUT score, and patient satisfaction) will be compared between groups via the generalized estimating equations (GEE) approach.

Change in KSS, and hospital length of stay will be compared between groups with two-sample t-tests or Wilcoxon rank-sum tests, depending upon the distribution of the data.

The success of blinding in each arm will be assessed with the Bang Blinding Index' (Bang H, Flaherty SP, Kolahi J, Park J. Blinding assessment in clinical trials: A review of statistical methods and a proposal of blinding assessment protocol. *Clin Res Regul Aff* 2010; 27:42-51.)

[Help](#)

[Help](#)

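### The primary stair-time comparison is unadjusted although age, pre-operative walking pain and pre-operative Knee Society Score are already collected, so available precision goes unused

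*Combined protocol and SAP*

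**What the plan says.** Sample Size and Data Analysis, item 3.0, states that the primary outcome, time to independent stair climbing, "will be compared between the periarticular injection alone and periarticular injection + ACB groups with a two-sample t-test or Wilcoxon rank-sum test", the choice depending on the distribution. Precision is to be "reported as a 95% confidence interval for the difference in means or the Hodges-Lehmann estimate of location shift". Neither route contains a covariate, and no adjusted model for this outcome appears elsewhere. The form's prompt for the same item asks the applicant to "Address how possible confounders will be identified and handled in analysis"; the answer names no variable.

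The Data Collection section lists, for the holding area on the day of surgery, "patient demographics (name, age, sex, race, BMI); NRS pain score at rest, during ambulation, while bending knee". It also lists "Knee Society Score - Both pre-operatively and at first post operative surgeon's office visit", taken from the Total Joint Registry. The secondary-outcome list likewise includes a pre-operative pain score and a pre-operative KSS.

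The Randomization section describes a computer-generated table and sealed opaque envelopes. It mentions no stratification on pre-operative function.

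**The concern.** The endpoint is a functional milestone, and no eligibility criterion sets a level of pre-operative walking or stair ability. Patients may therefore start from different levels of pain and function. The protocol's own rationale makes it plausible that this matters: the Background notes that quadriceps strength is already reduced before surgery, and the hypothesis is that less pain allows faster progress in physical therapy. That is an argument for prognostic value, not a measurement of it.

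If the three variables predict stair time, an unadjusted comparison leaves their contribution in the residual variance, and a chance imbalance in them passes into the estimate. With about 100 patients and one comparison on which the trial was sized, the result would be a wider interval for the difference in days than the collected data could give.

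**Working it through.** **Inputs from Sample Size and Data Analysis, item 2.0.** The SD is that found in a previous trial at the hospital "for TKR patients receiving periarticular injections to be 0.83 days". The effect is "A 0.5 day difference in mean time until patient is able to independently negotiate stairs". Two-sided alpha is 0.05, power 0.80, with 10% added. The stated result is 53 per group (106 in total), of whom 96 were expected to adhere to protocol; 92 of 106 did.

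**The plan's own figure.** A two-sample t-test with d = 0.5/0.83 = 0.602 needs 45 per group. Adding 10% gives 50 per group (100 in total), against the stated 53 (106). The stated figure is reached if a Wilcoxon efficiency allowance is included: 45 × π/3 = 47.1, rounded up to 48, and 48 × 1.1 = 52.8, rounded up to 53. The text does not mention this allowance. The gap is on the side of more patients and does not affect this point.

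**Unadjusted power and precision** (noncentral t; half-width = t(0.975, df) × 0.83 × √(2/n), n per group):
- 92 patients (46 per group): power 81.5%, 95% CI half-width 0.344 day.
- 96 patients (48 per group): standard error 0.83 × √(2/48) = 0.169 day, power 83.2%, half-width 0.336 day.
- If the Wilcoxon branch is used, the normal-theory efficiency of 3/π gives about 79.7% at 92 and 81.4% at 96, close to the target.

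**Effect of adjustment.** With N patients in total and k covariates of joint within-arm R-squared R², the variance of the estimated difference changes by about (1 − R²) × (1 + k/(N − k − 3)). The second factor is the expected cost of chance imbalance. With N = 96 and k = 3 it is 1 + 3/90 = 1.033. The documents give no R², so the values below are assumptions. Power and half-width also count the three degrees of freedom lost.

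| Assumed R² | Variance factor | Power at 96 | CI half-width (days) |
|---|---|---|---|
| Unadjusted | 1.00 | 83.2% | 0.336 |
| 0 | 1.033 | 81.9% | 0.342 |
| 5% | 0.95 × 1.033 = 0.98 | 83.8% | 0.333 |
| 10% | 0.90 × 1.033 = 0.93 | 85.7% | 0.325 |
| 20% | 0.80 × 1.033 = 0.83 | 89.5% | 0.306 |

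Worst case: √1.033 = 1.017, a standard error about 1.7% wider. Break-even: 1 − 1/1.033 = 0.032, or 0.033 once the lost degrees of freedom are counted.

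**Check by simulation** (92 patients, 6,000 replicates per setting): adjusted power was 84.1% at R² = 10% and 88.4% at 20%, against 81% to 82% unadjusted. The formula gives 84.1% and 88.1%.

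**The case against.** The strongest reply is that nothing here is wrong. Under randomisation the two-sample test is valid, its type I error and interval already allow for chance imbalance, and it matches the test named for the sample size. The power target is met without adjustment. The gain depends on an R² that the documents do not supply, and two features could keep it low. Stair ability is seen only at scheduled therapy sessions, so measured time is partly set by the timetable. Eligibility also narrows the population: planned discharge to rehabilitation, ASA IV, chronic opioid use, diabetes and disability are all excluded. All of this stands. It limits the point to efficiency and makes its size uncertain.

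It is also fair to say that a linear model replaces only the t-test branch. Session-based times will be tied and may be skewed, so the rank-based branch needs an adjusted counterpart.

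A reader might infer several stronger things that the documents do not support:
- *That enrolment was extended to 114 to gain precision, and that adjustment could take its place.* The stated purpose is to reach 96 patients without protocol deviations. Adjustment creates no adherent patients.
- *That randomisation was simple.* The Randomization section speaks only of a computer-generated table and does not say whether it was simple, blocked or stratified.
- *That the unanswered prompt on confounders shows confounding.* It is a generic form item in a randomised trial. It shows only that covariates were not addressed.

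**Conclusion.** The point holds as one of lost precision and exposure to chance imbalance. The primary analysis is unadjusted, three plausible pre-treatment covariates are already collected, and using them has a small, bounded downside. It does not show bias, an invalid test or a missed power target.

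The size rests on SD 0.83 days, 48 patients per group, three covariates and an assumed R². Between 5% and 20%, the variance falls by about 2% to 17% and power rises from 83% to between 84% and 89%. Below about 3% adjustment gains nothing, and at zero the standard error is about 1.7% wider. The change is worth making but is not essential to the validity of the trial.

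**What to change.** In item 3.0 of Sample Size and Data Analysis, before any unblinded look:
- Make the primary analysis a linear regression of stair time on arm, age, pre-operative NRS pain during ambulation and pre-operative KSS, with robust standard errors.
- Report the adjusted difference in mean days with its 95% confidence interval. This keeps the mean-difference scale on which the 0.5-day effect was set.
- Mean-impute any missing pre-operative value. This matters most for KSS, because the documents do not say how complete the registry is.
- Keep the unadjusted t-test, or the Wilcoxon test with the Hodges-Lehmann estimate, as a sensitivity analysis.
- Add a covariate-adjusted ordinal (proportional-odds) model as the rank-based counterpart, because times are session-based and may be tied or skewed.

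The cost is a short amendment and no new data. Because 106 patients had already been enrolled and their adherence assessed, the amendment should record that no outcome comparison by arm had been seen. The Data Safety Monitoring Plan states that no interim efficacy analysis is planned, which is consistent with making such a record.

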### 4.0 Identify and define the primary outcome and when the outcome will be measured. If measuring change in post-

Print: 2014-018 - The Combination of Adductor Canal Block and Periarticular Injection

... Page 5 of 37

<https://ecap.hss.edu/eCAP/ResourceAdministration/Project/PrintSmartForms?Project=cm.w...> 8/22/16

ID: 2014-018 Section: PART II - Clinical Research Proposal - Nature of Study

operative function is the most important, that will be your primary outcome.

Our primary outcome is time when patient is able to meet physical therapy discharge criteria, indicated by the ability to independently negotiate stairs- nonreciprocal (one leg at a time), with or without rails, and with or without assistive device (walker or cane). The primary outcome will be assessed during the morning, afternoon, and evening PT sessions of DOS, POD 1 and POD 2. The ability for a patient to meet discharge criteria after POD 2 will be assessed once a day as part of the standard PT visit.

5.0 Identify and define the secondary outcome(s) and when they will be measured (list additional goals one at a time with their corresponding outcomes).

- 1) NRS Pain Scores – pre op in the holding area, upon spinal resolution, 24 and 48 hours after Anesthesia end time
- 2) Incidence of nausea, dizziness, and vomiting - upon spinal resolution, 24 and 48 hours after Anesthesia end time
- 3) Incidence of pruritus - upon spinal resolution, 24 and 48 hours after Anesthesia end time
- 4) Patient satisfaction - upon spinal resolution, 24 and 48 hours after Anesthesia end time
- 5) PainOUT - upon spinal resolution, 24 and 48 hours after Anesthesia end time
- 6) Opioid consumption -24 and 48 hours after Anesthesia end time. With type and amount.
- 7) Hospital length of stay
- 8) KSS scores – acquired through the Total Joint Registry at the surgeon's office visit pre-operatively and approximately 6 weeks post operatively

Length of hospital stay and opioid consumption will be obtained from Clinics after the patient is discharged from the hospital.

[Help](#)

[Help](#)

**BACKGROUND** - Be sure to answer each question individually

1.0 Explain why these research questions are being asked:

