Hepatic or renal insufficiency

Patients younger than 18 years old and older than 80

Patients intending to receive general anesthesia

Patients planning to go to rehab post operatively  
Patients scheduled to go into the OR after the time agreed upon by Physical Therapist\*

Allergy or intolerance to one of the study medications  
Patients with an ASA of IV

Chronic gabapentin/pregabalin use (regular use for longer than 3 months)  
Chronic opioid use (taking opioids for longer than 3 months)

Diabetes

Patients on workers compensation or disability

\*Patients whose spinals are unlikely to resolve by 7:00 pm will be excluded from the study because it is not standard of care for physical therapists to see patients past 7:00 pm on the day of surgery.

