Postoperative analgesia will consist of: acetaminophen(10mg IV 1 hour post PACU admission), dexamethasone (10mg IV 1 hours post PACU admission), oxycodone (5 mg q 3 hr PRN), acetaminophen (1 g PO q 8 hr), ketorolac (15-30 mg IV q 6 hr X 4 doses), meloxicam daily (7.5mg PO if age 75 or older; 15 mg otherwise, to start after ketorolac is finished), dilauded (0.5 mg IV q 5 min X 4 PRN). In cases of severe pain (NRS scores greater than 6 for >2 hours), salvage therapy will be available using intravenous hydromorphone PCA. Orders for ondansetron (4 mg IV q 8 hr PRN) and metoclopramide (10 mg IV q 6 hr PRN) will also be placed, in case patients experience nausea.

Rehabilitation:

Patients participating in the study will have an accelerated rehab regimen until they meet Rehab goals for discharge. They will be seen by a physical therapist once on the day of surgery and then three times by a physical therapist (until they meet Rehab goals) on post operative day 1 and 2. If physical therapy (PT) discharge criteria are not met before POD 3, patients will default to the standard PT protocol (1 PT session + 1 Mobility technician session).

REHAB PROTOCOL:

1. Ambulation: WB: WBAT; walker, progress as appropriate; Day of Surgery- OOB to ambulate

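### Does the primary analysis need a stated rule for patients who never have a stair time recorded?

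*Combined protocol and SAP*

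**What the plan says.** Specific Aims, item 4.0, sets the assessment times: "The primary outcome will be assessed during the morning, afternoon, and evening PT sessions of DOS, POD 1 and POD 2". It then continues beyond the accelerated period: "The ability for a patient to meet discharge criteria after POD 2 will be assessed once a day as part of the standard PT visit". Item 5.0 adds hospital length of stay as a secondary outcome: "Length of hospital stay and opioid consumption will be obtained from Clinics after the patient is discharged from the hospital".

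Data Collection, item 1.0, has an item "was discharge criteria met (time and date" under POD 1 and POD 2. The day-of-surgery entry lists a physical therapy data sheet with stair details but not that item, and there is no in-hospital entry after POD 2. The list is not complete in itself: "Please see the data collection sheets for further detail".

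Sample Size and Data Analysis, item 3.0, compares the times "with a two-sample t-test or Wilcoxon rank-sum test, depending upon the distribution of the data" and gives no rule for a patient without a time. Item 2.0 of that section counts only protocol adherence. Data Safety Monitoring Plan, item 2.0, withdraws patients with toxicity complications but keeps them in hospital for observation; it does not mention their primary outcome.

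On the day of surgery, the Rehabilitation text in Interventions and Observations reads "They will be seen by a physical therapist once on the day of surgery", which differs from the three sessions implied in Specific Aims.

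**The concern.** A t-test or rank-sum test cannot use a blank. The protocol foresees two ways in which a blank could arise: the criterion is not met by discharge, or the patient is withdrawn for a complication. The first is slow recovery by definition; the second need not be. One blanket rule could therefore suit one group and distort the other. Leaving out slow patients removes the right tail, more often in the slower arm, and shrinks the difference. Entering withdrawn block patients as latest also shrinks it. An analyst who chose after seeing the data could move the estimate with two or three patients. If the time-and-date item really existed for only two days, the number of blanks could be larger.

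**Working it through.** **Inputs.** From Sample Size and Data Analysis, item 2.0: SD 0.83 day, difference 0.5 day, two-sided alpha 0.05, power 0.80, 10% added, 53 per group, 96 analysable patients (96/2 = 48 per arm). The documents give no expected number of patients without a stair time, so every count below is an assumption.

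**The plan's own figure.** Standardised difference 0.5/0.83 = 0.602. The exact two-sample t-test needs 44.24, so 45 per arm; 45 × 1.1 = 49.5, so 50 per arm, against 53 stated. The stated figure follows if 45 is scaled for a rank-sum test: 45 × π/3 = 47.1, so 48, and 48 × 1.1 = 52.8, so 53. For the t-test this leaves slack: power is 83.2% at 48 per arm and 80.7% at 45. Three times per arm lost at random would keep it above 80%.

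**Criterion not met by discharge, patients left out.** In the least favourable case, the k missing patients are the k latest controls. Dropping them lowers the control mean by 0.83 × S/(48 − k), where S is the sum of the expected k largest of 48 standard normal values (2.233, 1.837, 1.609).

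| k | S | Shift (day) | Difference seen (day) | t-test power (simulated) |
|---|---|---|---|---|
| 1 | 2.233 | 0.83 × 2.233/47 = 0.039 | 0.46 | 78% |
| 2 | 4.070 | 0.83 × 4.070/46 = 0.073 | 0.43 | 72% |
| 3 | 5.678 | 0.83 × 5.678/45 = 0.105 | 0.40 | 66% |

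Entering the same patients at the latest recorded time gives 0.49 to 0.50 day and 83% power.

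In a milder case, patients beyond a common discharge cutoff are dropped in both arms. If 1% or 2% of controls lie beyond it, the difference is 0.48 or 0.47 day and power is 82% or 80%. With skewed (gamma) times and shares of 2% to 10%, leaving out still shrinks the difference to 0.42 to 0.49 day, but power is not materially lower (82% to 92% against 82% to 83%).

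**Withdrawn for a complication.** If 1, 2 or 3 block patients are withdrawn for reasons unrelated to recovery, leaving them out keeps 0.50 day and 82% to 83% power. Entering them as latest gives 0.45, 0.40 or 0.35 day and 73%, 59% or 45%. If the complication itself delays recovery, leaving out is no longer neutral. With three of 48 delayed by 1 day, the difference in all randomised patients is 0.5 − 3 × 1/48 = 0.44 day; with a 2-day delay it is 0.5 − 3 × 2/48 = 0.375 day. Leaving them out still shows 0.50. The best handling therefore depends on an unknown, and no simple rule is right in every case.

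**How likely are blanks?** Three features keep the number down:

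- Late patients are assessed daily at the standard visit, and General Methods and Data Collection draw on medical records throughout the stay.
- The exclusion criteria remove "Patients planning to go to rehab post operatively", the group most likely to leave before managing stairs.
- Withdrawn patients stay under observation in the hospital, where a chart time can exist.

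**The recording list.** The day-of-surgery entry already captures stair details, and the criterion is stair negotiation. The data collection sheets are not reproduced, so the absence of one item from a summary list does not show that times go unrecorded.

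**Day-of-surgery sessions.** The order-set note under Pharmacy Involvement / Impact to EPIC, item 3.0, limits three-times-daily therapy to POD 1 and POD 2, in line with the Rehabilitation text. The Specific Aims sentence is the odd one out. The passages must be reconciled, but the analysis is the same under either reading.

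**The case for a change.** The strongest case for a change is that this is the only primary outcome, that the rule would take a few sentences, and that stating it in advance removes any freedom to choose after seeing the data. The margin is not wide either: only 92 of the first 106 patients adhered to protocol, and 96 are sought. With two or three unresolved patients in one arm, the choice between leaving out and entering as latest moves power by ten points or more.

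Part of this stands. The text has no rule, and stating one before the final analysis would be good practice. But the argument does not show that the plan as written goes wrong. The large losses come from placing all missing patients in one arm at the extreme of the distribution. For unresolved controls, leaving out biases towards no difference, so it would not manufacture a benefit. The one direction that could favour the block, leaving out complicated patients whose recovery was delayed, is also open under a rule that keeps late patients and drops withdrawn ones when no chart time can be had. Discharge time, worst rank, censoring and follow-up of all randomised patients are each defensible, and each has its own cost. Discharge time, for instance, is only a lower bound and gives 0.43 day when 20% of controls are unresolved and discharge times vary.

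**Conclusion.** No change is required. The plan omits a detail that a competent analyst fills in the ordinary way: recover the stair time from the chart where consent allows, treat patients not ready by discharge as late, check withdrawn patients both ways, and report counts by arm and reason. The data for this are already collected.

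The likely size is small: about 0.02 to 0.03 day and one to three points of power if 1% to 2% of controls are unresolved and left out. This rests on assumed counts, normal times with SD 0.83 and 48 per arm. If many patients turned out to have no stair time, or if complications clustered in the block arm and slowed recovery, the handling would matter and would need to be set out in the report. Nothing in the documents points to that. The differing day-of-surgery wording and the short recording list are editorial matters to reconcile and do not affect the comparison.

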### 2.0 What is/are the research question(s)/specific aim(s)? Pose very specific questions that can be addressed within the proposed design of the study. Prioritize them in order of importance.

Will the addition of an adductor canal block to peri-articular injections as an anesthetic regimen:

1. Allow for patients to achieve physical therapy discharge criteria earlier?
2. Reduce the pain NRS scores post-operatively?
3. Reduce the incidence of opioid related side effects?

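### Two secondary analyses leave collected baselines under-used: change in KSS is tested without baseline adjustment, and the NRS model does not say what role the pre-operative score plays

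*Combined protocol and SAP*

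**What the plan says.** **KSS.** Sample Size and Data Analysis, item 3.0, states: "Change in KSS, and hospital length of stay will be compared between groups with two-sample t-tests or Wilcoxon rank-sum tests". The choice between the two tests depends on the distribution, and no covariate is named. The secondary-outcome list (item 5.0, entry 8) takes KSS from the registry at the surgeon's "visit pre-operatively and approximately 6 weeks post operatively". Data Collection, item 1.0, agrees that both scores exist: "Knee Society Score - Both pre-operatively and at first post operative" office visit.

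**NRS.** The same analysis item groups NRS with other repeated measures, "Longitudinal secondary outcome data (NRS pain scores, narcotic consumption, incidence of side effects, painOUT score, and patient satisfaction", and compares them between groups by GEE. It gives no model terms, baseline term or main contrast. The secondary-outcome list gives the NRS times as "pre op in the holding area, upon spinal resolution, 24 and 48 hours after Anesthesia end time", so the pre-operative score stands in one line with the outcome times.

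Data Collection records the same three conditions before and after surgery. In the holding area it lists "patient demographics (name, age, sex, race, BMI); NRS pain score at rest, during ambulation, while bending knee". The first postoperative day begins "POD 1 - NRS pain score at rest, during ambulation, while bending knee; painOUT; opioid consumption". Spinal resolution and the second postoperative day carry the same three NRS items.

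Under Randomization, items 1.0 and 2.0, the anesthesiologist receives a sealed envelope at consent and it is opened in the operating room. The holding-area NRS therefore precedes disclosure of the allocation.

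**The concern.** A change score uses the baseline, but it fixes the slope of the post-operative on the pre-operative score at 1. If the true slope is lower, subtraction adds noise that a fitted slope would remove. ANCOVA needs only the two scores that the change score already needs.

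For NRS the issue is mainly specification. The pre-operative score could enter the GEE as a response, as a covariate or not at all, and these models have different precision. Post-operative pain is the second research question ("Reduce the pain NRS scores post-operatively"), so this matters more than KSS, which is last of eight secondary outcomes. An unstated model also leaves a choice that could be made after the data are seen.

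**Working it through.** **Inputs.** The documents give no power, SD or correlation for KSS or NRS, so the plan has no figure of its own to reproduce here. The stated 53 per group belongs to the primary outcome and is not in question. From the documents: 96 patients without protocol deviations, half in each group, so 48 per arm. Everything else below is assumed and shown as a range.

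**1. KSS: ANCOVA against the t-test on change.** Let k be the pre-operative SD divided by the post-operative SD, and rho the pre-post correlation. In units of the post-operative variance, the change score has variance k² + 1 − 2·rho·k and the ANCOVA residual has variance 1 − rho². The ratio is

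(1 − rho²) / (k² + 1 − 2·rho·k).

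| k | rho 0.3 | rho 0.5 | rho 0.7 | rho 0.8 |
|---|---|---|---|---|
| 0.8 | 0.78 | 0.89 | 0.98 | 1.00 |
| 1 | 0.65 | 0.75 | 0.85 | 0.90 |
| 1.25 | 0.50 | 0.57 | 0.63 | 0.64 |

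Example: k = 1, rho = 0.5 gives 0.75/1.00 = 0.75. With equal SDs the variance is 35/25/15% lower at rho 0.3/0.5/0.7, and the standard error 19/13/8% smaller. The denominator equals (k − rho)² + (1 − rho²), so the ratio cannot exceed 1 and equals 1 only when k = rho.

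Estimating the slope costs a little. In simulation at 48 per arm (20,000 runs, normal data) the ratios at k = 1 were 0.66/0.76/0.86, and 1.01 at k = rho = 0.8, a loss of about 1%. With HC3 robust errors the ANCOVA test rejected in 4.4 to 4.8% of runs under no effect.

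**2. KSS: ANCOVA against the Wilcoxon option.** The ratios above compare means only, so the rank test needs its own check. Simulated power at 48 per arm, equal SDs, assumed effects of 0.45 SD (rho 0.5) and 0.35 SD (rho 0.7):

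| Data | rho | Wilcoxon on change | ANCOVA, HC3 | Rank ANCOVA |
|---|---|---|---|---|
| t(3) errors | 0.5 | 77% | 74% | 87% |
| t(3) errors | 0.7 | 80% | 70% | 78% |
| Normal | 0.5 | 58% | 71% | – |
| Normal | 0.7 | 57% | 64% | – |

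Ordinary ANCOVA wins on normal data and loses on heavy-tailed data. On the heavy-tailed data, rank ANCOVA beats Wilcoxon at rho 0.5 and comes within 2 points of it at rho 0.7.

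**3. NRS: baseline as covariate against a post-operative-only, unadjusted GEE.** Let r be the correlation of the pre-operative score with each post-operative score, and c the correlation between post-operative scores. With equal post-operative SDs s, the mean of three times has variance s²(1 + 2c)/3, and adjustment multiplies it by 1 − 3r²/(1 + 2c). For a single time the factor is 1 − r².

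| r | Average of three (c = 0.5): variance reduction | Single time: variance reduction |
|---|---|---|
| 0.1 | 1.5% | 1% |
| 0.2 | 6% | 4% |
| 0.3 | 13.5% | 9% |
| 0.4 | 24% | 16% |

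At r = 0.4 the average gains 30% if c = 0.3 and 20% if c = 0.7.

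For scale, assume SD 2.5 and a difference of 1.0. The unadjusted variance is 6.25 × 2/3 = 4.167, so SE = √(2 × 4.167/48) = 0.417 and power Φ(1.0/0.417 − 1.96) = 67%. At r = 0.1/0.2/0.3/0.4 the SE is 0.414/0.404/0.388/0.363 and power 68/70/73/79%.

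**The case against.** The strongest reply is that a change-score comparison is a valid, pre-specified analysis of a minor outcome, and that preferring ANCOVA is a matter of taste. Validity stands in full. A reader might infer that the KSS test is biased or ignores the baseline. It does neither: subtraction uses the baseline, and randomization makes the comparison unbiased.

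Second, the plan allows Wilcoxon for awkward distributions, so a gain over the t-test is not a gain over the plan as written. This stands. The documents do not describe the distribution of KSS, and replacing both tests by ordinary ANCOVA could cost power. The rank option should be adjusted for baseline, not deleted.

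Third, the NRS comparator is assumed. A reader might infer that the planned GEE forfeits 13.5 or 24% of precision, or that it enters the pre-operative score as a response under a common group effect, which would dilute the estimate. The documents support neither, because the model terms are not given. If the baseline is already meant as a covariate, the gain is zero. The larger percentages also apply only to the average over three times, so a group-by-time model without a named contrast does not earn them.

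Fourth, adjustment can drop patients who lack a pre-operative NRS unless the plan says how to keep them. This also stands, and the fix covers it.

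**Conclusion.** The point holds as one of efficiency and specification in secondary outcomes. The primary analysis and the sample size are unaffected.

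For KSS, ANCOVA is asymptotically never less precise than the change-score t-test. The variance saving is 35/25/15% with equal SDs and rho 0.3/0.5/0.7, it vanishes when k equals rho, and the finite-sample loss is about 1% at worst. It would be wrong to read this as a gain in every case: with heavy tails, Wilcoxon on change can beat ordinary ANCOVA.

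For NRS, the firm conclusion is that the role of the pre-operative score must be stated. The added precision over an unadjusted post-operative model is small unless the pre-post correlation is about 0.3 or more. No size here can be fixed from the documents, since they give no KSS or NRS SDs or correlations.

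**What to change.** Amend item 3.0 of Sample Size and Data Analysis:

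1. **KSS.** Analyse 6-week KSS by ANCOVA with pre-operative KSS as covariate and robust standard errors. Where the distribution would have led to Wilcoxon, use a baseline-adjusted rank analysis (rank ANCOVA) in its place.
2. **NRS.** Fit the GEE to spinal resolution, 24 h and 48 h only, with the matching pre-operative score (rest, ambulation or bending) as covariate, plus time, group and group-by-time. Name the group effect averaged over the three times as the main contrast. Keep patients who lack a baseline score, for example by mean imputation of the baseline.

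The cost is a few sentences of wording and, at worst, about 1% of variance for the estimated KSS slope. Both baselines are already collected, so no patients, visits or measurements are added.
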